6. ANALYSES AND SUMMARIES

Data collected before baseline will only be listed, unless otherwise stated.

For all endpoints, baseline is defined in Section 3.

For Cohorts 1 and 2, End of Treatment is defined as Week 26. For Cohort 3, End of Treatment is defined as Week 32.

Data from participants enrolled into the original cohort (Cohort 1) and Cohort 2 will be combined for reporting, where data from the placebo and 2-week titration arms will be combined from the 2 cohorts and analyzed together. Data from participants enrolled into Cohort 3 will be analyzed and reported separately unless otherwise specified.

6.1. Primary Endpoint(s)

6.1.1. Percent Change from Baseline in Body Weight at End of Treatment

6.1.1.1. Main Analysis

In all cases the Estimand Set 1, as specified in Section 2.2.1 will be utilised.

Absolute changes from baseline and percent changes from baseline in body weight will be summarised descriptively by treatment group and time point as described in Section 5.2.1, which will be presented separately for the combined Cohorts 1 & 2 and Cohort 3. Tables will present all data from the screening (visit 1, absolute tables only), beginning of the placebo run-un (visit 2, absolute tables only), baseline and post-baseline time points (including follow-up, which will be restricted to participants who completed treatment up to and including the End of Treatment visit).

The primary analysis will be an MMRM (as described in Section 5.2.3) applied to the changes from baseline in body weight on the natural log scale at Weeks 2, 4, 6, 8, 10, 12, 16, 18, 22 and 26 for Cohorts 1 & 2, and at Weeks 4, 8, 12, 16, 20, 24, 28 and 32 for Cohort 3, that will be used to estimate the treatment effect related to the primary Estimand 1 (as described in Section 2.2.1). The MMRM results will be back-transformed as described in Section 3.1 for presentations.

The following results from the above primary analysis will be plotted separately for the combined Cohorts 1 & 2 and Cohort 3 and for Cohorts 1, 2 and 3 combined. The plots for Cohort 1 & 2 and Cohort 3 separately will not be included in the CSR.

- Profile plots of the back-transformed LSMeans (including 90% confidence intervals) representing percent change from baseline over time, with a separate line for each treatment group
- Profile plots of the back-transformed LSMean differences to Placebo (including 90% confidence intervals), representing percent change to Placebo over time, with a separate line for each treatment group of danuglipron
- Plot of the back-transformed LSMeans (including 90% confidence intervals) representing percent change from baseline at End of Treatment versus treatment group on the x-axis (applicable to analyses related to body weight only)
- Plot of the back-transformed LSMean differences to Placebo (including 90% confidence intervals) representing percent change to Placebo at End of Treatment, with a separate point for each treatment group of danuglipron (applicable to analyses related to body weight only)

PFIZER CONFIDENTIAL DMB02-GSOP-RF02 8.0 *Statistical Analysis Plan Template* TMF Doc ID: 98.03 Page 31 of 61 Standard SAS output will be provided to support the main statistical summary table for the primary analysis model but will not be included in the CSR.

Statistical Model Diagnostics

The presence of outliers will be investigated for this analysis. An outlier will be defined as any response data value with a studentized (conditional) residual greater than 3, or less than -3. A listing will be presented of any participants meeting these criteria and will be included with standard SAS outputs. The assumptions of normality will be verified graphically using residual plots. For each fitted model, a set of conditional studentized residual plots will be produced, including residual plot, histogram of normality, QQ plot and summary of fit statistics. The residual plots will not be included in the clinical study report.

If there are outliers or major deviations from normality, then the effect of these on the conclusions may be investigated through alternative transformations and/or analyses excluding outliers. Justification for any alternative to the planned analysis will be given in the report of the study.

6.1.1.2. Sensitivity/Supplementary Analyses

For all of the following analyses, standard SAS output will be provided to support the statistical summaries produced but will not be included in the CSR.

The following supplementary analyses to the primary endpoint will be carried out:

- To assume a dose-response relationship with body weight (without a baseline interaction) an Emax model will be applied to the raw LSMeans at End of Treatment from the main MMRM analysis as described in Section 5.2.5. Final results from the Emax model will be back transformed using the same formula as provided in 3.1. This will only be applied in reference to percent change from baseline in body weight for Cohorts 1 & 2.
- To assume a dose-response relationship with body weight, including an interaction between baseline body weight and dose, an Emax model will be applied to the raw LSMeans at End of Treatment from separate MMRM models at the overall baseline body weight as described in Section 5.2.6. Final results from the Emax model will be back transformed using the same formula as provided in 3.1. This will only be applied in reference to percent change from baseline in body weight for Cohorts 1 & 2.
- To model absolute changes from baseline in body weight, a separate MMRM model (as described in Section 5.2.3) will be applied to the absolute change from baseline in body weight at Weeks 2, 4, 6, 8, 10, 12, 16, 18, 22 and 26 for Cohorts 1 & 2, and at Weeks 4, 8, 12, 16, 20, 24, 28 and 32 for Cohort 3 separately, where baseline absolute body weight will be the baseline term. Similar outputs to Section 6.1.1.1 will be reported from the MMRM model where back-transformation of LSMeans and LSMean differences will not be applicable, along with standard SAS output (which will not be included in the CSR).

The additional exploratory estimand to the primary endpoint will be carried out:

An additional exploratory analysis that assesses the primary endpoint in evaluable participants with no major protocol deviations while on treatment (Section 2.2.3) will be performed to estimate the treatment effect related to the exploratory Estimand 7 (as described in Section 2.2.3). The same summary and analysis output as the main analysis (Section 6.1.1.1) will be performed and reported but applied to the Estimand Set 2 (as described in Section 4).

6.2. Secondary Endpoint(s)

6.2.1. Response as defined by a body weight loss of ≥5% from baseline at End of Treatment

In all cases the Estimand Set 1 as specified in Section 4 will be utilised.

The proportion of responses at End of Treatment will be summarised descriptively by treatment group as described in Section 5.2.2, where no imputation for missing values will be conducted. The proportion of responses at End of Treatment will also be reported after multiple imputation for missing values as per Section 5.3.

A logistic regression model (as described in Section 5.2.4) will be applied to the response at End of Treatment that will be used to estimate the treatment effect related to the secondary Estimand 2 (as described in Section 2.2.2.1), where missing values will be imputed using multiple imputation as per Section 5.3. Baseline body weight and strata will be included in the model.

In addition, standard SAS output will be provided to support the main statistical summary table for the logistic regression model and multiple imputation approach but will not be included in the CSR.

6.2.2. Percent CFB in Body Weight over time

In all cases a dataset similar to Estimand Set 1 as specified in Section 4 will be utilised.

Percent CFB in body weight will be summarized at Weeks 2, 4, 6, 8, 10, 12, 16, 18 and 22 for Cohorts 1 & 2 and for Weeks 4, 8, 12, 16, 20, 24 and 28 for Cohort 3. Summaries and analysis results will be reported as part of the main analysis approach for the primary endpoint (Section 6.1.1.1).

6.2.3. Absolute CFB in waist circumference at End of Treatment

In all cases a dataset similar to Estimand Set 1 as specified in Section 4 will be utilised.

Absolute changes from baseline in waist circumference will be summarised and analysed similar to body weight in Section 6.1.1.1, including follow-up.

An MMRM (as described in Section 5.2.3) will be applied to the absolute change from baseline at Weeks 2, 4, 6, 8, 10, 12, 16, 18, 22 and 26 for Cohorts 1 & 2 and at Weeks 4, 8, 12, 16, 20, 24, 28 and 32 for Cohort 3 separately, where baseline waist circumference will be the baseline term. Results similar to body weight in Section 6.1.1.1, where back-transformation of LSMeans and LSMean differences will not be applicable, will be reported along with standard SAS output (where the figures and standard SAS output will not be included in the CSR).

PFIZER CONFIDENTIAL DMB02-GSOP-RF02 8.0 *Statistical Analysis Plan Template* TMF Doc ID: 98.03 Page 33 of 61 The MMRM results from the End of Treatment visit will be extracted in order to estimate the treatment effect related to Estimand 3.

6.2.4. Absolute CFB in waist-to-hip ratio at End of Treatment

In all cases a dataset similar to Estimand Set 1 as specified in Section 4 will be utilised.

Absolute changes from baseline in waist-to-hip ratio will be summarised and analysed similar to body weight in Section 6.1.1.1, including follow-up.

An MMRM (as described in Section 5.2.3) will be applied to the absolute change from baseline at Weeks 2, 4, 6, 8, 10, 12, 16, 18, 22 and 26 for Cohorts 1 & 2 and at Weeks 4, 8, 12, 16, 20, 24, 28 and 32 for Cohort 3 separately, where baseline waist-to-hip ratio will be the baseline term. Results similar to body weight in Section 6.1.1.1, where back-transformation of LSMeans and LSMean differences will not be applicable, will be reported along with standard SAS output (where figures and standard SAS output will not be included in the CSR).

The MMRM results from the End of Treatment visit will be extracted in order to estimate the treatment effect related to Estimand 4.

6.2.5. Absolute CFB in HbA1c

In all cases a dataset similar to Estimand Set 1 as specified in Section 4 will be utilised.

Absolute changes from baseline in HbA1c will be summarised and analysed similar to body weight (Weeks 16 and 26 for Cohorts 1 & 2 and Weeks 16, 24 and 32 for Cohort 3) in Section 6.1.1.1, including follow-up.

An MMRM (as described in Section 5.2.3) will be applied to the absolute change from baseline at the time points specified above where baseline HbA1c will be the baseline term. Results similar to body weight in Section 6.1.1.1, where back-transformation of LSMeans and LSMean differences will not be applicable, will be reported along with standard SAS output (where figures and standard SAS output will not be included in the CSR).

The MMRM results will be extracted in order to estimate the treatment effect related to Estimand 5.

6.2.6. Absolute CFB in FPG over time

In all cases a dataset similar to Estimand Set 1 as specified in Section 4 will be utilised.

Absolute changes from baseline in FPG will be summarised and analysed similar to body weight in Section 6.1.1.1, including follow-up.

An MMRM (as described in Section 5.2.3) will be applied to the absolute change from baseline at Weeks 2, 4, 6, 8, 10, 12, 16, 18, 22 and 26 for Cohorts 1 & 2 and separately, at Weeks 4, 8, 12, 16, 20, 24, 28 and 32 for Cohort 3, where baseline FPG will be the baseline term. Results similar to body weight in Section 6.1.1.1, where back-transformation of LSMeans and LSMean differences will not be applicable, will be reported along with standard SAS output (where figures and standard SAS output will not be included in the CSR).

PFIZER CONFIDENTIAL DMB02-GSOP-RF02 8.0 *Statistical Analysis Plan Template* TMF Doc ID: 98.03 Page 34 of 61 The MMRM results will be extracted in order to estimate the treatment effect related to Estimand 6.

6.3. Other Safety Summaries and Analyses Endpoint(s)

The AEs of interest are defined in Section 3.2.2.1.1. Figures described in this section may not be included in the CSR.

6.3.1. Adverse Events

Adverse events (Tier 1, 2 and 3 AEs as described in Section 3.2.2.1) will be summarized by treatment group and overall and in accordance with sponsor reporting standards using the safety analysis set defined in Section 4. The adverse events (AEs) will be sorted in descending frequency within a system organ class.

Incidence and severity of treatment emergent adverse event (TEAE) tables will additionally be produced ('All causality' and 'Treatment related', separately) to summarise the total number of adverse events by preferred term, which will be reported by treatment group and overall.

The following tables and figures related to TEAEs classed as Tier 1 or 2 will be ordered in descending point estimate of risk difference within System Organ Class. If two or more events have the same frequency, they will be sorted alphabetically by preferred term.

TEAEs classed as Tier 1 events will be tabulated by treatment group. Number of participants and percent will be presented, along with the risk difference between each treatment group of danuglipron and placebo. 95% confidence intervals and p-values will also be presented for the comparison. No adjustment for multiplicity will be used.

Tier 1 TEAEs will also be presented graphically. The TEAEs will be presented in a two-panel plot, the left panel will give the proportions of TEAEs observed in a treatment group of danuglipron and separately placebo while the right panel will display the 95% confidence interval for the risk differences for each TEAE. A vertical line corresponding to the value of 0 will be added to the right-hand plot. For the graphical display for tier 1 events, a column containing the p-value for each event will be added to the right-hand side of the forest plot in the right panel. Each panel will be paged by treatment group of danuglipron.

TEAEs classed as Tier 2 events will be summarised and graphically presented similar to Tier 1 events, but no p-values will be presented. No adjustments for multiplicity will also be used.

For Tier 1 and Tier 2 outputs, footnotes will be included on the tables to provide proper interpretation of p-values (Tier 1 only) and confidence intervals and to describe how the comparison was conducted, e.g. "P-values and confidence intervals are not adjusted for multiplicity and should be used for screening purpose only. 95% Confidence intervals are provided to help gauge the precision of the estimates for Risk Difference. Risk Difference is computed as danuglipron versus placebo."

The incidence of TEAEs by preferred term with more than 5% occurrences by preferred term will be presented. The TEAEs to include in tables will be based on those occurring in more than 5% of participants in either (1) Cohorts 1 and 2 combined; or (2) more than 5% of participants in Cohort 3.

PFIZER CONFIDENTIAL DMB02-GSOP-RF02 8.0 *Statistical Analysis Plan Template* TMF Doc ID: 98.03 Page 35 of 61 TEAEs with more than 5% occurrences in any treatment arm will additionally be presented, split by the titration step at the time of TEAE onset.

It should be recognized that most studies are not designed to reliably demonstrate a causal relationship between the use of a pharmaceutical product and an adverse event or a group of adverse events. Except for select events in unique situations, studies do not employ formal adjudication procedures for the purpose of event classification. As such, safety analysis is generally considered as an exploratory analysis and its purpose is to generate hypotheses for further investigation. The 3-tier approach facilitates this exploratory analysis.

6.3.1.1. Forest plots on the Incidence of adverse events of interest

Forest plots displaying the incidence of TEAEs of interest ("All Causality" only) by treatment group will be produced separately by AE. Each forest plot will present all treatment groups separately and will include 95% confidence intervals (calculated using the Blyth-Still-Casella method⁹).

6.3.1.2. Incidence of first occurrence of adverse events of interest by week

The number and percentage of participants who experience the first occurrence of a TEAE of interest each week (up to and including the follow-up visit) will be tabulated by treatment group and week, where percentage will be defined in two ways. These will be included in the same table and produced separately for each TEAE of interest.

To calculate the percentage each week, the numerator will be the total number of participants with the TEAE of interest that was also their first post-dose occurrence of the event during that respective week. The two approaches for the denominator are: (1) the total overall number of evaluable participants in the Safety Analysis Set for the respective treatment group; and (2) the total number of participants who had not discontinued from the study prior to that respective week will be the denominator (note if a participant did discontinue from the study during that respective week they would be included in the denominator).

A figure of the percentage per week will also be produced, with week on the x-axis and a separate line for each treatment group. The percentage will represent the above definition (2) of the denominator but based on blinded data reviews this figure may be adapted or additionally produced based on definition (1). These figures will be produced separately for each TEAE of interest.

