7. DISCONTINUATION OF STUDY INTERVENTION AND PARTICIPANT DISCONTINUATION/WITHDRAWAL

7.1. Discontinuation of Study Intervention

It may be necessary for a participant to permanently discontinue study intervention. Reasons for permanent discontinuation of study intervention include the following:

- Criteria for a potential Hy's law case are met (see Appendix 6);
- Intent to become pregnant or pregnancy confirmed by β-hCG testing;
- Safety or tolerability concern arises, in particular if not responsive to symptomatic management, dosing with double-blind study intervention may be stopped in an individual participant at the discretion of the investigator;
- Based on mental health assessment as outlined in Section 8.2.6, should be discontinued from dosing at the discretion of the investigator.

If the criteria for permanent discontinuation are met, the site should notify the sponsor Medical Monitor or sponsor Clinician.

Note that discontinuation of study intervention does not represent withdrawal from the study. If study intervention is definitively discontinued, the participant will remain in the study to be evaluated for obesity, and will be expected to continue with all study visits and assessments as outlined in the SoA for the applicable cohort (see SoA for Cohorts 1 and 2, and SoA for Cohort 3), with the exception of dosing activities and assessment of PK. See the SoA for the applicable cohort (see SoA for Cohorts 1 and 2, and SoA for Cohort 3) for data to be collected at the time of discontinuation of study intervention and follow-up for any further evaluations that need to be completed.

In the event of discontinuation of study intervention, it must be documented on the appropriate CRF/in the medical records whether the participant is discontinuing further receipt of study intervention or also from study procedures, posttreatment study follow-up, and/or future collection of additional information.

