3.2.2. Safety Endpoint(s)

3.2.2.1. Adverse Event

If an adverse event has a start time of 00:00 and a start date that is equal to the date of first administration of IP, the adverse event start time will be imputed with the time of the first dose of administration of IP.

If an adverse event has an end time of 00:00 then the end time will be imputed as 23:59.

An adverse event is considered treatment emergent (TEAE) relative to a given treatment if the event starts during the effective duration of treatment (i.e. starting on or after the first dose but before the last dose plus lag time).

The effective duration of treatment is determined by the lag time. Any event occurring within the lag time, whether this occurs during a break in treatment or at the end of treatment, is attributed to the corresponding treatment period. The lag time is defined by the Pfizer Standard of 365 days post last dose of IP.

Adverse events occurring during the placebo run-in period (i.e. starting from Day -14, inclusive, up to and before the first dose of active treatment on Day 1) will be considered non-treatment emergent.

A 3-tier approach will be used to summarize TEAEs. Under this approach, TEAEs are classified into 1 of 3 tiers. Different analyses will be performed for different tiers (see Section 6.3.1.

Tier 1 events: These are prespecified events of clinical importance and are maintained in a list in the product's Safety Review Plan.

Tier 2 events: These are events that are not tier 1 but are "common." A Medical Dictionary for Regulatory Activities (MedDRA) preferred term (PT) is defined as a Tier 2 event if there are at least 5% of participants reporting the event in any of the standard titration or placebo groups or at least 2 participants reporting the event in any of the slow titration groups.

Tier 3 events: These are events that are neither Tier 1 nor Tier 2 events.

PFIZER CONFIDENTIAL DMB02-GSOP-RF02 8.0 *Statistical Analysis Plan Template* TMF Doc ID: 98.03 Page 17 of 61

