6.3.1.3. Prevalence of adverse events of interest by week

The number and percentage of participants who are experiencing a TEAE of interest (either onset or ongoing) each week (up to and including the follow-up visit, with week as appropriate based on the End of Treatment definition) will be tabulated by treatment group and week. A separate table representing the number and percentage by severity (mild, moderate or severe) will also be produced. These tables will be produced separately for each TEAE of interest.

To calculate the percentage each week, the total number of participants who experience the TEAE of interest at any time during the respective week will be the numerator and the total number of participants who had not discontinued from IP and/or the study prior to that

PFIZER CONFIDENTIAL DMB02-GSOP-RF02 8.0 Statistical Analysis Plan Template TMF Doc ID: 98.03 Page 36 of 61 respective week will be the denominator (note if a participant did discontinue from IP and/or the study during that respective week they would be included in the denominator).

A figure of the overall percentage (i.e. not by severity) per week will be produced, with week on the x-axis and a separate line for each treatment group. A separate figure of the percentage per week will also be produced, with week on the x-axis and a separate line for each severity, paged by treatment group. These figures will be produced separately for each TEAE of interest.

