6.3.1.4. Time to First Occurrence/Recurrence of AEs of Interest

Exploratory summaries on the time to the first occurrence of AEs of interest will be produced in Cumulative Incidence Plots as described in Section 5.2.7. Participants who discontinue from the study or discontinue from IP prior to the start of the AE event of interest will be censored at the discontinuation/initiation date.

A separate plot for each AE of interest will be produced separately.

The above will also be produced separately for the time to the first recurrence of the AEs of interest.

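### SAP 6.3.1.2: the default denominator for weekly first occurrence keeps participants who already had the event, so later-week onset reads too low, most in arms with many early events

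*SAP*

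**What the plan says.** SAP 6.3.1.2 plans a table by arm and week, running through follow-up, for each adverse event of interest (nausea, vomiting and diarrhoea, per SAP 3.2.2.1.1). The numerator is "the total number of participants with the TEAE of interest that was also their first post-dose occurrence of the event during that respective week". Two percentages are given:

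- Denominator (1) is "the total overall number of evaluable participants in the Safety Analysis Set for the respective treatment group".
- For denominator (2), "the total number of participants who had not discontinued from the study prior to that respective week will be the denominator". Someone who leaves during the week still counts.

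For the figure, the SAP states: "The percentage will represent the above definition (2) of the denominator". It adds that blinded review may lead to a version based on (1), instead or as well.

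Four other places bear on who is counted:

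- Protocol 7.1: "Note that discontinuation of study intervention does not represent withdrawal from the study". Such participants are expected to keep attending visits.
- SAP 6.3.1.3 (weekly prevalence) divides by "the total number of participants who had not discontinued from IP and/or the study prior to that" week.
- SAP 6.3.1.4 (time to first occurrence): "Participants who discontinue from the study or discontinue from IP prior to the start of the AE event of interest will be censored".
- SAP 3.2.2.1 (treatment-emergent window): "The lag time is defined by the Pfizer Standard of 365 days post last dose of IP".

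**The concern.** The numerator of 6.3.1.2 can be filled only by people who have not yet had the event. Denominator (2) drops those who left the study but keeps everyone who has already had a first event. As events accumulate, a growing part of it cannot contribute to the numerator, and this part grows fastest in the arm with the most early events.

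A line per arm by week invites a reading as the timing of gastrointestinal onset. Timing matters here: Protocol 4.2 says Cohorts 2 and 3 were added to characterize tolerability and efficacy under 2-week and 4-week titration steps, and Protocol 4.3 suggests that 4-week steps may ease gastrointestinal effects. In an arm with many early events, a line that falls because few event-free people remain could be taken for adaptation to the drug.

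**Working it through.** **Inputs.** The definitions are those of the SAP and protocol sections cited. For scale only, Protocol 9.2 gives about 60 randomized per 1-week titration arm, about 25 expected completers per 2-week arm, and 25% drop-out. The plan states no figure for this output, so there is nothing to reproduce. The following are assumed because the documents do not give them:

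- *h*: weekly onset among those who can still have a first event, set at 5%
- *E*: share with a prior event, 10% to 60%
- *d*: share of the arm that has left the study
- *s*: share of the arm off IP but still in the study

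**Step 1: prior events alone.** The percentage under (2) is *h* × (event-free in study ÷ all in study). If having had the event is unrelated to leaving the study, *d* cancels and this is *h* × (1 − *E*). In an arm of 60 with nobody gone:

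- *E* = 10%: 54 event-free, 54 × 0.05 = 2.7 first events, 2.7/60 = 4.5%.
- *E* = 50%: 30 event-free, 30 × 0.05 = 1.5 first events, 1.5/60 = 2.5%.

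| Share with prior event | Shown under (2) | With event-free denominator |
|---|---|---|
| 10% | 4.50% | 5.00% |
| 30% | 3.50% | 5.00% |
| 50% | 2.50% | 5.00% |
| 60% | 2.00% | 5.00% |

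**Step 2: two arms.** With the same true 5% in both, and *E* of 10% on placebo and 50% on active, the figure shows 4.50% and 2.50%. The order can reverse. A true 3.5% on placebo and 5.0% on active show as 3.5 × 0.9 = 3.15% and 5.0 × 0.5 = 2.50%.

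**Step 3: if prior cases leave the study more often.** Let *f* be the fraction of prior cases who have left, with no other exits. The factor becomes (1 − *E*)/(1 − *fE*). At *E* = 50% it is 0.50, 0.57, 0.67 and 1.00 for *f* = 0, 25%, 50% and 100%. The understatement disappears only if every prior case has left.

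**Step 4: participants off IP but in the study.** Two cases bracket this part.

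- They have no further first events, and stopping is unrelated to prior events: the percentage is *h* × (1 − *E*) × (1 − *s*/(1 − *d*)). With *d* = 10% and *s* = 15% the last factor is 1 − 0.15/0.90 = 0.833. This gives 3.75% at *E* = 10% and 2.08% at *E* = 50%.
- They have the same onset as everyone else: their first events enter the numerator through the 365-day window, and the result returns to *h* × (1 − *E*), or 2.50% at *E* = 50%. Only the prior-event part remains.

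In the first case, borrowing the 6.3.1.3 rule alone (dropping those off IP) brings the result back only to 4.50% and 2.50%. It does not remove prior cases.

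**Step 5: precision after the change.** With 25 in the study and *E* = 50%, about 12.5 are event-free, so one event reads 1/12.5 = 8% instead of 1/25 = 4%. With 45 in the study (60 × 0.75), it reads 1/22.5 = 4.4% instead of 2.2%.

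**The case against.** The SAP never calls this percentage a rate or a hazard. It reports a count and two openly defined percentages, so understatement exists only if the reader takes the figure as onset among those at risk. Denominator (1) also keeps prior cases. That is fair, and it is why the point is limited to that reading. But (1) has a clear meaning: a share of the arm, whose weekly counts build up to the number ever affected. Denominator (2) is neither a share of the arm nor a percentage of those at risk.

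Other planned outputs address timing. SAP 6.3.1.4 gives cumulative incidence plots with a proper risk set, and SAP 6.3.1 splits events seen in more than 5% of any arm by titration step at onset. SAP 6.3 says its figures may not reach the clinical study report, and SAP 6.3.1 describes safety analysis as generally exploratory. All of this stands and lowers the stakes, but none of it changes or labels this table and figure.

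A reader might infer that keeping participants off IP is itself an error, or that 6.3.1.2 contradicts 6.3.1.3. The documents do not support either. With a treatment-emergent window of 365 days, a first event after stopping IP validly counts, and a study-based denominator fits that definition. Prevalence is a different quantity and may have a different denominator.

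Finally, an event-free denominator is not a clean comparison either. If participants differ in susceptibility, those still event-free in a high-event arm are the more tolerant ones. This limits how far the corrected figure can be interpreted; it does not justify keeping prior cases in.

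**Conclusion.** The point holds for prior events. Read as onset over time, denominator (2) understates later weeks by a factor of about (1 − share with a prior event), and by more in arms with many early events. The factor assumes that prior events are unrelated to leaving the study; if prior cases leave more often, the effect shrinks. The direction follows from the definitions. The size does not: the 5% onset and the 10% to 60% shares are assumptions.

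The IP part is conditional. It matters only if on-treatment onset is the intended quantity, and 6.3.1.2 does not say so.

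A reader might go further and infer that the comparison of titration schemes is compromised, or that an early-event arm will be declared safer. The documents do not support that. No test or decision rule uses this output, other outputs show onset timing, and the reversal in Step 2 is a possibility under assumed rates, not a forecast. This is a minor correction to a descriptive safety display, with no bearing on the primary analysis.

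**What to change.** In SAP 6.3.1.2, redefine denominator (2) as Safety Analysis Set participants who, at the start of the week, are still in the study and have not yet had the event. Use it for the figure, and print the number at risk for each week and arm.

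State whether on-treatment onset is intended. If it is, also remove participants who prematurely discontinued IP from numerator and denominator alike, in line with the censoring in 6.3.1.4. Participants who completed treatment and are in follow-up should not be treated as having discontinued.

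Keep denominator (1), labelled as a share of the arm, so that its counts still reconcile with the treatment-emergent event tables.

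The cost is a sentence or two in the SAP and a denominator filter. Late-week denominators become smaller and the percentages noisier, which is why the number at risk should be shown. If the on-treatment version is chosen, its weekly counts will no longer match the full event tables, and a footnote should say so.
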